
#### 3.2.4.2 Withdrawal of consent to trial participation

Patients may withdraw their consent to trial participation at any time without the need to justify the decision.

If a patient wants to withdraw consent, the investigator should be involved in the discussion with the patient and explain the difference between trial treatment discontinuation and withdrawal of consent to trial participation, as well as explain the options for continued follow-up after trial treatment discontinuation, please see Section [3.2.4.1](#) above. This discussion, as well as the patient's decision, should be well documented in the source.

#### 3.2.4.3 Discontinuation of the trial by the sponsor

Boehringer Ingelheim reserves the right to discontinue the trial overall or at a particular site at any time for the following reasons:

1. New efficacy or safety information invalidating the earlier positive benefit–risk assessment.
2. Violation of GCP, the trial protocol, or the contract impairing the appropriate conduct of the trial.
3. Marketing authorization of spesolimab i.v.

Trial site will be reimbursed for reasonable expenses incurred in case of trial termination (except in case of the second reason).

## 4. TREATMENTS

### 4.1 INVESTIGATIONAL TREATMENTS

#### 4.1.1 Identity of the Investigational Medicinal Product

All patients will be treated with spesolimab in this trial. There is no active comparator or placebo.

Table 4.1.1: 1 Spesolimab

Substance:	Spesolimab (BI 655130)
Pharmaceutical formulation:	Solution for infusion
Source:	Boehringer Ingelheim Pharma GmbH & Co KG
Unit strength:	Spesolimab 450 mg/vial (60 mg/mL), 7.5 mL fill volume
Posology:	900 mg single i.v dose
Method and route of administration:	i.v infusion

#### 4.1.2 Drug assignment and administration of doses for each patient

Trial medication kits will be assigned to patients via Interactive Response Technology (IRT) system after verification of all inclusion and exclusion criteria, and patient will receive spesolimab 900 mg i.v at Visit 2 (Day 1). If flare symptoms persist after a single infusion of study medication, a second infusion (900 mg i.v. spesolimab) is allowed at Visit 3 (Day 8) per investigator's discretion and the medication number of the second dose will be also assigned via IRT system.

An Interactive Response Technology (IRT) will be used to screen eligible patients, assign medication kits and manage initial/re-supply ordering of drug supplies. The investigator will receive all necessary instructions to access the IRT from the Sponsor. Detailed IRT functions and procedures will be documented in the user requirement specifications mutually agreed to by the sponsor and the IRT vendor.

Site personnel will enter the medication numbers in the eCRF. Note that the patient number is different from the medication number (the former is generated during screening via the IRT System). Each medication kit (containing 2 vials) will have a unique medication number.

Detailed instructions for administration of spesolimab i.v. are provided in the ISF.

#### **4.1.3 Packaging, labelling, and re-supply**

The investigational medicinal products will be provided by BI or a designated CRO. They will be packaged and labelled in accordance with the principles of Good Manufacturing Practice (GMP). The investigational product consists of a carton holding 2 vials of the trial medication. Each carton will have a unique medication number.

Shipment and re-supply of trial medication to the local depots and/or sites will be managed via an IRT system, which will also monitor expiry dates of available supplies.

For details of packaging and the description of the label, refer to the ISF.

#### **4.1.4 Storage conditions**

Drug supplies will be kept in their original packaging and in a secure limited access storage area according to the recommended storage conditions on the medication label. A temperature log must be maintained for documentation. Trial medication must be securely stored, e.g. in a locked refrigerator or at a pharmacy. If the storage conditions are found to be outside the specified range, the Clinical Research Associate (CRA) (as provided in the list of contacts) must be contacted immediately. Refer to the ISF for additional information.

The trial medication must be administered in the manner specified in the trial protocol and instructions for IMP preparation handling and administration of spesolimab.

#### **4.1.5 Drug accountability**

The primary investigator or designee will receive the investigational drugs delivered by the sponsor when the following requirements are fulfilled:

- Approval of the clinical trial protocol by the IRB / ethics committee.
- Availability of a signed and dated clinical trial contract between the sponsor and the investigational site.
- Approval/notification of the regulatory authority, e.g. competent authority.
- Availability of the curriculum vitae of the Principal Investigator.
- Availability of a signed and dated clinical trial protocol.

Investigational drugs are not allowed to be used outside the context of this protocol. They must not be forwarded to other investigators or clinics.

All unused trial medication must be returned to the sponsor. All used and partially used medication must be destroyed locally by the trial site. Receipt, usage and return or disposal must be documented on the respective forms. Account must be given for any discrepancies.

The primary investigator or designee must maintain records of the product's delivery to the trial site, the inventory at the site, the use by each patient, and the return to the sponsor or warehouse / drug distribution centre or alternative disposal of unused products. If applicable, the sponsor or warehouse / drug distribution centre will maintain records of the disposal.

These records will include dates, quantities, batch / serial numbers, expiry ('use-by') dates, and the unique code numbers assigned to the investigational medicinal product and patients participating in the trial. The primary investigator or designee will maintain records that document adequately that the patients were provided the doses specified by the trial protocol and reconcile all investigational medicinal products received from the sponsor. At the time of return to the sponsor or appointed CRO, the primary investigator or designee must verify that all unused drug supplies have been returned by the clinical trial staff and all used or partially used supplies have been destroyed by the trial site, and that no remaining supplies are in the primary investigator's possession.

## **4.2 OTHER TREATMENTS, EMERGENCY PROCEDURES, RESTRICTIONS**

### **4.2.1 Other treatments and emergency procedures**

All concomitant therapies will be recorded on the appropriate pages of the electronic CRF (eCRF).

#### **4.2.1.1 Emergency procedures**

##### Systemic hypersensitivity including infusion reactions and anaphylactic reaction

In case of systemic hypersensitivity, including infusion reactions and anaphylactic reaction, emerging during or after infusion of investigational medication, the investigator should consider, in accordance with severity of the reaction and local standard of care, to:

- Immediately interrupt the infusion
- Treat with systemic antihistamines, i.v. steroids, and in case of a severe allergic reaction (e.g., anaphylactic reaction) epinephrine
- Refer the patient to an emergency unit

In case of systemic hypersensitivity including infusion reactions, based on the patient's clinical course and the physician's medical judgment, the infusion may be re-initiated in case of mild or moderate systemic hypersensitivity, including infusion reactions (according to NCI grading, grade 1 or 2), at a slower speed with a gradual increase to complete the infusion as detailed in the Instructions for Preparation and Handling of spesolimab in the ISF. In all cases, the total duration of infusion should not exceed 180 minutes (3 hours).

In case of anaphylactic reactions based on published criteria (Appendix [10.1](#); [R11-4890](#)), the investigator should discontinue treatment with spesolimab.

When a delayed hypersensitivity reaction is suspected, in addition to drawing a blood sample for laboratory assessment (complete blood count with differential, comprehensive metabolic panel (includes liver enzymes), LDH, immune complexes profile), please evaluate for signs of extra-cutaneous organ involvement. The decision to discontinue treatment and/or restart treatment after resolution of the reaction should be based on reaction type and severity.

In case of potential systemic allergic reaction: where possible, blood samples for determination of serum tryptase, as well as histamine, IgE and serum complement component assay, should be collected 0.5 h, 2 h, 6 h, 24 h after onset of the event.

Any clinically meaningful changes in laboratory values should be reported as an AE, SAE or AESI (as appropriate).

Severe infections (according to RCTC grading the ISF), serious infections, opportunistic or mycobacterium tuberculosis infections

Treatment of the infection should be initiated promptly according to local standard of care.

Active/Latent TB:

A suitable TB test, according to local regulations will be performed at screening. If the result is positive, the patient may participate in the trial if further work up (according to local practice/guidelines) establishes conclusively that the patient has no evidence of active tuberculosis. Active TB patients must be excluded. If the presence of latent tuberculosis is established, then treatment should have been initiated and maintained according to local country guidelines. If the TB test results are not available at the time of infusion, these patients may receive treatment (provided they meet all other inclusion/exclusion criteria) as long as the investigator has ruled out active disease based on available documented history (i.e. negative for active TB) within 3 months prior to infusion.

Malignancies

In case of occurrence of malignant neoplasm other than appropriately treated basal cell carcinoma or squamous cell carcinoma of the skin or in situ carcinoma of uterine cervix, treatment discontinuation is to be a consideration if deemed clinically appropriate by the investigator. In addition, diagnostics and treatment are to be initiated according to local standard of care.

## 4.2.2 Restrictions

### 4.2.2.1 Restrictions regarding concomitant treatment

The medications (or classes of medications) listed in [Table 4.2.2.1: 1](#) must not have been taken before infusion for the time periods as specified

Table 4.2.2.1: 1 Restricted medications

Medication or class of medications	Restriction duration
IL-36R inhibitors (other than spesolimab provided in the trial)	4 weeks prior to any infusion and not until after 16 weeks after last infusion of spesolimab
Live vaccinations	
Anakinra (or other IL-1/IL-1R inhibitors)	Not to be administered concurrently with spesolimab

#### 4.2.2.2 Restrictions on diet and lifestyle

No specific restrictions on diet or lifestyle of the patients are required.

#### 4.2.2.3 Contraception requirements

Women of childbearing potential must use highly effective methods of birth control per ICH M3 (R2) that result in a low failure rate of less than 1% per year when used consistently and correctly. A list of contraception methods meeting these criteria is provided in the Patient Information.

## 5. ASSESSMENTS

### 5.1 ASSESSMENT OF EFFICACY

This is an open-label trial with no active or placebo control. Efficacy will not be evaluated.

### 5.2 ASSESSMENT OF SAFETY

Safety will be assessed descriptively based on the occurrence of:

- Treatment emergent adverse events (TEAEs)
- Treatment emergent serious adverse events (SAEs)
- Treatment emergent adverse events of special interest (AESIs).

No confirmatory safety analysis is planned.

#### 5.2.1 Physical examination

A complete physical examination will be performed before first drug administration at the time points specified in the [FLOW CHART](#). Examination includes, at a minimum, general appearance, neck, lungs, cardiovascular system, abdomen, extremities, and skin. Measurement of height and body weight should also be performed.

Physical examination will be performed at follow-up visits according to standard clinical practice and when deemed appropriate by the investigator.

The results must be included in the source documents available at the site.

#### 5.2.2 Vital signs

Vital signs will be evaluated before first drug administration at the time points specified in the Flow Chart. This includes measuring temperature, pulse rate and systolic/diastolic blood pressure. Pulse rate and blood pressure will be measured after patients have been sitting comfortably for at least 5 minutes.

Vital signs will be evaluated at follow-up visits according to standard clinical practice and when deemed appropriate by the investigator.

The results must be included in the source documents available at the site.

#### 5.2.3 Safety laboratory parameters

The laboratory tests listed in [Table 5.2.3:1](#) are to be collected at the trial sites and assessed by the investigators prior to study drug infusion for eligibility confirmation.

Any additional laboratory testing during the trial is optional and should be performed at the discretion of the investigator in accordance with the current standard of care, which may yield useful information for the management and safety evaluation of the patient.

Clinically relevant abnormal findings as judged by the investigator will be reported as adverse events (please refer to section [5.2.4](#)).

In case the criteria for DILI are fulfilled, a number of additional measures will be performed (please see section [5.2.4.1.4](#) and the DILI Checklist provided in the ISF).

Table 5.2.3:1 Laboratory tests to be assessed at V1 prior to i.v. administration (Local Labs)

Category	Test name
Haematology	Haematocrit Haemoglobin Red blood cell count (RBC) White blood cell count (WBC) Platelet count
WBC differential (relative and absolute)	Neutrophils, eosinophils, basophils, monocytes, lymphocytes
Enzymes	Aspartate transaminase (AST/GOT) Alanine transaminase (ALT/GPT) Alkaline phosphatase
Substrates	Total bilirubin
Infection testing	Hepatitis B Surface Antigen Hepatitis B Surface Antibody Hepatitis B core Antibody HBV-DNA (quantitative)  QuantiFERON® TB or T-Spot®  Hepatitis C Antibodies HIV-1, and HIV-2 Antibody
Serum Pregnancy test (only for female patients of childbearing potential)	Human Serum Chorionic Gonadotropin

 An HBV-DNA test should be conducted if Hepatitis B core Antibody and/or Hepatitis B Surface Antibody is positive and Hepatitis B Surface Antigen is negative. If HBV DNA level is undetectable (<2.1 log copies/mL) at screening, the patient can participate in this trial.

 If the 1st QuantiFERON® TB or T-Spot® test result is indeterminate, a retest should be performed.

## 5.2.4 Assessment of adverse events

### 5.2.4.1 Definitions of AEs

#### 5.2.4.1.1 Adverse event

An AE is defined as any untoward medical occurrence in a patient or clinical investigation subject administered a medicinal product and which does not necessarily have to have a causal relationship with this treatment.

An AE can therefore be any unfavourable and unintended sign (including an abnormal laboratory finding), symptom, or disease temporally associated with the use of a medicinal product, whether related or not.

The following should also be recorded as an AE in the CRF and BI SAE form (if applicable):

- Worsening of the underlying disease or of other pre-existing conditions
- Changes in vital signs, ECG, physical examination and laboratory test results, if they are judged clinically relevant by the investigator.

If such abnormalities already exist prior to trial inclusion, they will be considered as baseline conditions and should be collected in the eCRF only.

#### 5.2.4.1.2 Serious adverse event

A serious adverse event (SAE) is defined as any AE which fulfils at least one of the following criteria:

- results in death,
- is life-threatening, which refers to an event in which the patient was at risk of death at the time of the event; it does not refer to an event that hypothetically might have caused death if more severe,
- requires inpatient hospitalisation or prolongation of existing hospitalisation,
- results in persistent or significant disability or incapacity,
- is a congenital anomaly / birth defect,
- is deemed serious for any other reason if it is an important medical event when based on appropriate medical judgement which may jeopardise the patient and may require medical or surgical intervention to prevent one of the other outcomes listed in the above definitions. Examples of such events are intensive treatment in an emergency room or at home for allergic bronchospasm, blood dyscrasias or convulsions that do not result in hospitalisation or development of dependency or abuse.
- An event that possibly leads to disability will be handled as ‘deemed serious for any other reason’ and, therefore, reported as an SAE.

#### 5.2.4.1.3 AEs considered “Always Serious”

In accordance with the European Medicines Agency initiative on Important Medical Events, Boehringer Ingelheim has set up a list of AEs, which by their nature can always be considered to be “serious” even though they may not have met the criteria of an SAE as defined above.

The latest list of “Always Serious AEs” can be found in the eDC system. A copy of the latest list of “Always Serious AEs” will be provided upon request. These events should always be reported as SAEs as described in Section [5.2.4.2](#).

Cancers of new histology and exacerbations of existing cancer must be classified as a serious event regardless of the time since discontinuation of the drug and must be reported as described in [5.2.4.2](#), subsections “AE Collection” and “**AE reporting to sponsor and timelines**”.

#### 5.2.4.1.4 Adverse events of special interest

The term adverse events of special interest (AESI) relates to any specific AE that has been identified at the project level as being of particular concern for prospective safety monitoring and safety assessment within this trial, e.g. the potential for AEs based on knowledge from other compounds in the same class. AESIs need to be reported to the sponsor's Pharmacovigilance Department within the same timeframe that applies to SAEs, please see section [5.2.4.2.2](#).

The following are considered as AESIs:

#### Potential Severe Drug Induced Liver Injury (DILI)

A potential severe Drug Induced Liver Injury (DILI) that requires follow-up is defined by the following alterations of hepatic laboratory parameters:

- An elevation of AST and/or ALT  $\geq 3$ -fold ULN, combined with an elevation of total bilirubin  $\geq 2$ -fold ULN measured in the same blood sample, or in samples drawn within 30 days of each other, or
- ALT, and/or AST elevations  $\geq 10$ -fold ULN

These lab findings constitute a hepatic injury alert and the patients showing these lab abnormalities need to be followed up according to the "DILI checklist" provided in the ISF. In case of clinical symptoms of hepatic injury (icterus, unexplained encephalopathy, unexplained coagulopathy, right upper quadrant abdominal pain, etc.) without lab results (ALT, AST, alkaline phosphatase, total bilirubin) available, the investigator should make sure these parameters are analysed, if necessary, in an unscheduled blood test. Should the results meet the criteria of hepatic injury alert, the procedures described in the DILI checklist should be followed.

#### Systemic hypersensitivity reactions including infusion reactions and anaphylactic reaction

Any suspicion of severe systemic hypersensitivity including infusion reactions and any anaphylactic reaction should be defined and assessed using the criteria discussed in the statement paper from Sampson et al. (Section [4.2.1.1](#) and Appendix [10.1, R11-4890](#)).

#### Severe infections (according to RCTC grading in the ISF)

##### Opportunistic and mycobacterium tuberculosis infections

These include pneumocystis jirovecii, BK virus disease including PVAN, CMV, posttransplant lymphoproliferative disorder (EBV), progressive multifocal leucoencephalopathy, bartonellosis (disseminated only), blastomycosis, toxoplasmosis, coccidioidomycosis, histoplasmosis, aspergillosis (invasive only), candidiasis (invasive or pharyngeal), cryptococcosis, other invasive fungi (mucormycosis (zygomycosis, rhizopus, mucor, lichtheimia), scedosporium/pseudallescheria boydii, fusarium), legionellosis, listeria monocytogenes (invasive only), tuberculosis, nocardiosis, non-tuberculous mycobacterium, salmonellosis (invasive only), HBV reactivation, herpes simplex (invasive only), herpes zoster, strongyloides (hyperinfection syndrome and disseminated forms only),

paracoccidioides, penicillium marneffeii, sporothrix schenckii, cryptosporidium species (chronic only), microsporidiosis, leishmaniasis (visceral only), trypanosoma cruzi infection (Chagas' disease) (disseminated only), campylobacteriosis (invasive only), shigellosis (invasive only), vibriosis (invasive due to vibrio vulnificus), HCV progression ([R17-2617](#)).

#### Peripheral neuropathy

Any event suspected or diagnosed as Peripheral Neuropathy is considered as an AESI. For the treatment interruption rules, please see section [3.2.4.1](#)

#### 5.2.4.1.5 Intensity (severity) of AEs

The intensity (severity) of adverse events should be classified and recorded in the CRF according to the RCTC version 2.0 (refer to ISF for details).

#### 5.2.4.1.6 Causal relationship of AEs

Medical judgement should be used to determine the relationship between the adverse event and the BI investigational compound, considering all relevant factors, including pattern of reaction, temporal relationship, de-challenge or re-challenge, confounding factors such as concomitant medication, concomitant diseases and relevant history.

Arguments that may suggest that there is a reasonable possibility of a causal relationship could be:

- The event is consistent with the known pharmacology of the drug.
- The event is known to be caused by or attributed to the drug class.
- A plausible time to onset of the event relative to the time of drug exposure.
- Evidence that the event is reproducible when the drug is re-introduced.
- No medically sound alternative aetiologies that could explain the event (e.g. pre-existing or concomitant diseases, or co-medications).
- The event is typically drug-related and infrequent in the general population not exposed to drugs (e.g. Stevens-Johnson syndrome).
- An indication of dose-response (i.e. greater effect size if the dose is increased, smaller effect size if dose is reduced).

Arguments that may suggest that there is no reasonable possibility of a causal relationship could be:

- No plausible time to onset of the event relative to the time of drug exposure is evident (e.g. pre-treatment cases, diagnosis of cancer or chronic disease within days / weeks of drug administration; an allergic reaction weeks after discontinuation of the drug concerned).
- Continuation of the event despite the withdrawal of the medication, considering the pharmacological properties of the compound (e.g. after 5 half-lives).  
Of note, this criterion may not be applicable to events whose time course is prolonged despite removing the original trigger.
- There is an alternative explanation, e.g. situations where other drugs or underlying diseases appear to provide a more likely explanation for the observed event than the drug concerned.

- Disappearance of the event even though the trial drug treatment continues or remains unchanged.

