#### *Residual Effect Period*

The Residual Effect Period (REP) of spesolimab is 16 weeks. This is the period after the last dose with measurable drug levels and/or pharmacodynamic effects still likely to be present.

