Systemic hypersensitivity reaction	After administration of any biologic agent or protein, there is a possibility of occurrence of immediate (such as anaphylaxis) or delayed (such as drug reaction with eosinophilia and systemic symptoms) adverse immune reactions.	Patients with a history of allergy/hypersensitivity to spesolimab or its excipients are excluded from the trial. In case of systemic hypersensitivity reactions including anaphylactic reaction emerging during or after administration of spesolimab, the investigator should consider, in accordance with severity of the reaction and local standard of care, interruption of therapy and treatment of the condition. Systemic hypersensitivity reaction is defined as an AESI. It is subject to close monitoring and investigators are requested to assess these conditions using the criteria discussed in the statement paper from Sampson et al. [ R11-4890 ].

Table 1.4: 1 Risks associated with spesolimab administration (cont.)

Risks of clinical relevance for this trial	Summary of data, rationale for the risk	Mitigation strategy
Infections	
Inhibition of the immune response with an immune-modulating biologic may increase the risk of infections.
 
In clinical trials with spesolimab, a higher proportion of patients with mild to moderate infections was seen in the spesolimab treatment group than in the placebo treatment group.
 
Nevertheless, there was no indication of an increased frequency of patients with severe, serious, and opportunistic infections in association with spesolimab treatment.
 
A recent characterisation of individuals with homozygous IL36R KO mutations revealed that normal immune function was broadly preserved, suggesting that IL36 signalling pathway inhibition may not substantially compromise host defenses [R17-3632].
	
Patients with any relevant chronic or acute infections including HIV, viral hepatitis or active tuberculosis are excluded from the trial. Treatment of infections should be initiated promptly according to standard of care.
 
Severe infections and opportunistic infections are considered AESI for this trial. These conditions and serious infections are subject to close monitoring.

Table 1.4: 1 Risks associated with spesolimab administration (cont.)

Risks of clinical relevance for this trial	Summary of data, rationale for the risk	Mitigation strategy

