#### 5.2.4.2 Adverse event collection and reporting

##### 5.2.4.2.1 AE Collection

The investigator shall maintain and keep detailed records of all AEs in the patient files. The following must be collected and documented on the appropriate CRF(s) by the investigator:

- From signing the informed consent onwards until the individual patient's end of study (16 weeks after last dose of spesolimab, or at the time of withdrawal of participation): all AEs (serious and non-serious) and all AESIs.
- After the individual patient's end of study: the investigator does not need to actively monitor the patient for new AEs but should only report any occurrence of cancer and trial drug-related SAEs and trial drug-related AESIs of which the investigator may become aware of by any means of communication, e.g. phone call. Those AEs should however not be reported in the CRF.
- Upon patient re-entry into the trial, the patient should be re-evaluated to ensure that eligibility criteria are still met and the overall trial is still running in order to assess AEs (serious and non-serious) and AESIs.

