#### **7.1.1 Safety analyses**

In general, safety analyses will be descriptive in nature and will be based on BI standards. No hypothesis testing is planned.

Adverse events will be coded using the Medical Dictionary for Drug Regulatory Activities (MedDRA). Standard BI summary tables and listings will be produced. Statistical analysis and reporting of adverse events will concentrate on treatment-emergent adverse events, i.e. all adverse events occurring between start of treatment and end of the REP, a period of 16 weeks after the last dose of trial medication. Adverse events that start before first drug intake and deteriorate under treatment will also be considered as 'treatment-emergent'. All adverse events with an onset between start of treatment and end of the REP, a period of 16 weeks after the last dose of trial medication, will be assigned to the on-treatment period for evaluation.

All treated patients will be included in the safety analysis.

Frequency, severity, and causal relationship of adverse events will be tabulated by system organ class and preferred term. after coding according to the current version of the Medical Dictionary for Drug Regulatory Activities (MedDRA) at database lock.

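### The causality guidance cites a late allergic reaction as having no plausible onset, which conflicts with the protocol's own 16-week residual effect period and its named risk of delayed hypersensitivity

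*Combined protocol and SAP*

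**What the plan says.** Section 5.2.4.1.6 begins with a general instruction: "Medical judgement should be used to determine the relationship between the adverse event and the BI investigational compound, considering all relevant factors". Two lists of arguments follow. The second is introduced by "Arguments that may suggest that there is no reasonable possibility of a causal relationship could be". Its first item concerns onset that is not plausible relative to drug exposure, and one of the examples is "an allergic reaction weeks after discontinuation of the drug concerned". Its last item is "Disappearance of the event even though the trial drug treatment continues or remains unchanged". Only one item in that list, on events that continue after withdrawal, refers to the compound's pharmacology, with five half-lives as its yardstick.

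Other sections describe the drug and its risks as follows.

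- Synopsis and section 3.1: treatment is one infusion, with an optional second one week later.
- Section 1.2.1: the half-life is about three weeks in GPP and about four weeks in healthy volunteers. The REP is 16 weeks and is defined thus: "This is the period after the last dose with measurable drug levels and/or pharmacodynamic effects still likely to be present".
- Table 1.4:1: the systemic hypersensitivity row covers immediate reactions and "delayed (such as drug reaction with eosinophilia and systemic symptoms) adverse immune reactions".
- Section 4.2.1.1: there is a specific laboratory and organ work-up for suspected delayed hypersensitivity.
- Section 7.1.1: adverse events with onset up to 16 weeks after the last dose belong to the on-treatment period.

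Causality is used in two places. Section 7.1.1 states: "Frequency, severity, and causal relationship of adverse events will be tabulated by system organ class and preferred term". Section 5.2.4.2.1 says that after the patient's end of study the investigator "should only report any occurrence of cancer and trial drug-related SAEs and trial drug-related AESIs". The Vital Status paragraph in the same section applies a similar limit to the 16-week phone contact for early stoppers, while requiring all deaths and cancers.

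**The concern.** Treatment is over on Day 1 or Day 8, so a site could regard nearly all of follow-up as time after the drug was stopped. A hypersensitivity reaction at week 3 or 4 would fit the protocol's risk table and fall inside both the REP and the on-treatment window. It would also resemble the example that 5.2.4.1.6 gives of timing that speaks against the drug. Worked examples are there to steer judgement, and this one steers away from a risk that the protocol itself names.

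At stake are the counts of related events in a trial whose secondary aim is additional safety data, and the reporting of some SAEs and AESIs through the routes that ask for them only when they are rated drug-related.

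**Working it through.** The trial has no recruitment goal and no hypothesis test, so there is no planned figure to reproduce. The check is whether a reaction weeks after the last infusion occurs with drug still present.

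**Inputs.** Half-life h = 3 weeks (GPP) or 4 weeks (healthy volunteers), and REP = 16 weeks, all from section 1.2.1. Second infusion one week after the first, from section 3.1.

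**Assumption.** Mono-exponential decline, ignoring the distribution phase and any effect of anti-drug antibodies.

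**Formulas**, with t in weeks after the last infusion and the result as a share of one full dose:

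- one infusion: 0.5^(t/h)
- two infusions one week apart: 0.5^(t/h) + 0.5^((t+1)/h)

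At t = 4 and h = 3, one infusion gives 0.5^(4/3) = 0.397. Two infusions give 0.397 + 0.5^(5/3) = 0.397 + 0.315 = 0.712.

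| Weeks after last infusion | One infusion, h = 3 | One infusion, h = 4 | Two infusions, h = 3 | Two infusions, h = 4 |
|---|---|---|---|---|
| 2 | 63.0% | 70.7% | 113.0% | 130.2% |
| 3 | 50.0% | 59.5% | 89.7% | 109.5% |
| 4 | 39.7% | 50.0% | 71.2% | 92.0% |
| 8 | 15.7% | 25.0% | 28.2% | 46.0% |
| 16 | 2.5% | 6.25% | 4.4% | 11.5% |

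Five half-lives are 5 × 3 = 15 to 5 × 4 = 20 weeks. The REP is 16/3 = 5.3 or 16/4 = 4.0 half-lives. The one pharmacological yardstick in 5.2.4.1.6 is therefore of the same order as the REP, while the allergic-reaction example, counted only in weeks, falls well inside it.

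**Where a wrong rating would have an effect.**

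- Primary and secondary endpoints (sections 2.1.2 and 2.1.3): none, because occurrence of TEAEs, SAEs and AESIs is counted whatever the causality.
- Reporting to the sponsor within 24 hours (5.2.4.2.2): none during the trial, because SAEs and AESIs are reported whatever the causality.
- Causality tables (7.1.1): affected directly.
- After end of study (5.2.4.2.1): affected. For completers this starts at 16 weeks, when 2.5% to 6.25% of a single dose remains. The same section also ends the study at withdrawal of participation. A patient who withdraws two weeks after a single infusion would come under the limit with about 63% to 71% of the dose present.
- The 16-week phone contact for early stoppers (5.2.4.2.1, Vital Status): affected for SAEs and AESIs other than deaths and cancers.

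**The case against.** The strongest reply is that the list decides nothing. It is worded permissively, medical judgement over all relevant factors comes first, and the opposing list includes a plausible time to onset and the drug's known pharmacology. The protocol gives sites the half-life, the REP and the delayed-reaction risk, so a site that reads the whole document is told such reactions can be drug-caused. This stands, and it rules out a stronger reading that a reader might infer, namely that the guidance does bias sites toward rating events unrelated. The documents contain no evidence on how sites rate, and the percentages above measure residual drug, not misclassification.

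A second reply is that the protocol mostly uses discontinuation for stopping early (Flow Chart footnote 2, section 3.2.4), not for completing a planned infusion. That may narrow the patients to whom a site applies the example. It does not remove the conflict, because someone who stops early also carries drug for weeks after the last dose.

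A third concerns the item on events that disappear while treatment goes on. A reader might take it as a second source of bias, since a transient event could resolve while drug is still circulating. The documents do not support that. With one or two infusions no treatment is continuing, so the item is inapplicable, and it would mislead only if a site took a completed infusion for unchanged treatment.

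Finally, section 3.2.4.1 asks that new or changed adverse events be recorded where possible at the 16-week contact. This softens the limit for early stoppers but leaves the mandatory minimum as it is.

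**Conclusion.** The point holds in a limited form. The allergic-reaction example conflicts with sections 1.2.1, 4.2.1.1 and 7.1.1 and with Table 1.4:1, and these should be reconciled. It could lead to under-attribution of delayed immune reactions, but the size of any shift cannot be computed from the documents. At 4 weeks after a single infusion about 40% to 50% of the dose remains, given the stated half-lives and mono-exponential decline, so such timing is not implausible by the protocol's own account.

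The effect is confined to the descriptive causality tables and to the drug-related-only reporting in 5.2.4.2.1. A reader might infer that the trial's safety endpoints, or SAE and AESI reporting during the trial, are compromised. They are not, because neither depends on causality. This is a cheap improvement to existing guidance.

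**What to change.** In section 5.2.4.1.6, delete the allergic-reaction example and add one sentence: for this trial, plausibility of onset is judged with the patient regarded as exposed throughout the 16-week REP after the last infusion. A cross-reference to section 1.2.1, Table 1.4:1 and section 4.2.1.1 would complete the reconciliation.

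Do not re-anchor the example to onset after the end of the REP. For completers, the drug-related-only reporting begins at that point, so the new wording would label late reactions implausible in the very route that depends on their being recognised.

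Optionally, note that the argument about an event disappearing while treatment continues does not apply to one- or two-infusion treatment.

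The cost is a few sentences in the protocol and a short item in site training. The downside is that somewhat more events may be rated drug-related and sent for expedited assessment.
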